8.9 Health Economics Medical Resource Utilization and Health Economics

Health Economics OR Medical Resource Utilization and Health Economics are not evaluated in this study.

8.10 Visit Requirements

Visit requirements are outlined in Section 1.3. Specific procedure-related details are provided in Section 8.

8.10.1 Screening

Screening procedures will be conducted at Visit 1 (Day 1) as outlined in Section 1.3.

Screening procedures may be repeated after consultation with the Sponsor.

8.10.2 Treatment Period/Vaccination Visit

Requirements during the treatment period are outlined in Section 1.3.

8.10.3 Discontinued Participants Continuing to be Monitored in the Study

Participants who receive a single-dose intervention cannot discontinue study intervention.

9 STATISTICAL ANALYSIS PLAN

This section outlines the statistical analysis strategy and procedures for the study. If, after the study has begun, but prior to any unblinding, changes are made to primary and/or key secondary hypotheses, or the statistical methods related to those hypotheses, then the protocol will be amended (consistent with ICH Guideline E-9). Changes to exploratory or other non-confirmatory analyses made after the protocol has been finalized, but prior to unblinding, will be documented in an sSAP and referenced in the CSR for the study. Post hoc exploratory analyses will be clearly identified in the CSR.

9.1 Statistical Analysis Plan Summary

Key elements of the statistical analysis plan are summarized below; the comprehensive plan is provided in Section 9.2 through Section 9.12.

Study Design Overview	A Phase 2, Randomized, Double-Blind, Multicenter Study to Evaluate the Safety and Immunogenicity of Three Different Potency Levels of V181 (Dengue Quadrivalent Vaccine rDENVΔ30 [live, attenuated]) in Healthy Adults
Treatment Assignment	There are 4 vaccination arms. Participants will be assigned randomly in a 2:4:4:1 ratio to the V181 High Potency Level Group, V181 Mid Potency Level Group, V181 Low Potency Level Group, or Placebo using an IRT. A double-blind/masking technique will be used.
Analysis Populations	Immunogenicity: Per-Protocol Population Safety: All Participants as Treated (ApdT)
Primary Endpoint(s)	Immunogenicity (Primary): Dengue virus-neutralizing antibody GMTs for each of the 4 dengue serotypes at Day 28 postvaccination as measured by the VRNT Safety (Primary): Vaccine-related serious adverse events (SAEs) from Day 1 through Day 28 postvaccination
Key Secondary Endpoints	Safety (Secondary): 
Solicited injection-site adverse events (AEs) of pain, erythema, and swelling from Day 1 through Day 5 postvaccinationSolicited systemic AEs of rash, headache, fatigue (tiredness), myalgia (muscle pain), and arthralgia (joint pain) from Day 1 through Day 28 postvaccination
Statistical Methods for Key Immunogenicity Analyses	To address the primary immunogenicity non-inferiority objective, the comparison between groups will be made based on serotype-specific GMTs for the 4 dengue serotypes at Day 28 postvaccination. The estimation of the GMT ratios and the corresponding 95% CIs will be calculated using a linear model with the log-transformed antibody titer as the response and a single term for vaccination group.

Statistical Methods for Key Safety Analyses	The analysis of safety results will follow a tiered approach. The tiers differ with respect to the analyses that will be performed. Adverse events (specific terms as well as SOC terms) are either prespecified as “Tier 1” endpoints or will be classified as belonging to “Tier 2” or “Tier 3” based on the number of events observed. There are no Tier 1 events for this protocol. Tier 2 parameters will be assessed via point estimates with 95% CIs provided for differences in the proportion of participants with events (Miettinen and Nurminen [M&N] method [1985] [Miettinen, O. and Nurminen, M. 1985]). Safety endpoints that are not Tier 1 or 2 events are considered Tier 3 events. Only point estimates by vaccination group are provided for Tier 3 safety parameters.
Interim Analyses	There are no planned interim analyses for this study.
Multiplicity	No multiplicity adjustment is needed for this study as success is required on all 4 dengue serotypes.
Sample Size and Power	The overall sample size will be approximately 1265 with 230 participants in the high potency group, 460 participants in each of the mid and low potency groups, and 115 participants in the placebo group. The study has an overall power of >95% to establish that the V181 Low Potency Level is non-inferior to the V181 Mid Potency Level for all four serotypes at an overall one-sided, 2.5% alpha-level.

9.2 Responsibility for Analyses/In-house Blinding

The statistical analysis of the data obtained from this study will be the responsibility of the Clinical Biostatistics department of the Sponsor. This study will be conducted as a double-blind study under in-house blinding procedures.

The Clinical Biostatistics department will generate the randomized allocation schedule(s) for study treatment assignment. Randomization will be implemented in an IRT. The primary safety and immunogenicity evaluation period for this study is defined as the period from Day 1 through Day 28 postvaccination. A CSR will be produced to present the results for this time period in order to inform potency specifications for the V181 vaccine. The official, final database for the Day 28 analysis will not be unblinded until medical/scientific review has been performed, protocol deviations have been identified, and data have been declared final and complete. After the Day 28 postvaccination visit, participants will be followed for safety (SAEs and deaths only) and immunogenicity through Month 12 postvaccination. Results from the Day 28 through Month 12 postvaccination time period will be presented in a final, separate study report.

After database lock for the primary analysis, most Sponsor Headquarters personnel involved in the conduct of the trial will be unblinded to vaccination group assignments. A blinded

medical monitoring team will monitor the study after Day 28 through Month 12 postvaccination. Investigators, study site personnel, participants, and Sponsor field personnel or delegate(s) (eg, Clinical Research Associate) will remain blinded to treatment group assignments until the final study analyses are completed following the Month 12 (final) database lock.

9.3 Hypotheses/Estimation

Objectives and hypotheses of the study are stated in Section 3.0.

9.4 Analysis Endpoints

Immunogenicity and safety endpoints that will be evaluated are listed below.

9.4.1 Immunogenicity and ^{CCI} Endpoints

Primary Immunogenicity Endpoint

- Dengue virus-neutralizing antibody GMTs for each of the 4 dengue serotypes at Day 28 postvaccination as measured by VRNT.

CCI

9.4.2 Safety Endpoints

An initial description of safety measures is provided in Section 4.2.1.2. The overall safety and tolerability profile for each vaccine will be assessed by clinical review of all safety data collected. Solicited and unsolicited injection-site and systemic AEs will be summarized overall, and by maximum reported intensity. The primary safety evaluation period for this study will be Day 1 through Day 28 postvaccination.

Primary Safety Endpoints

- Vaccine-related SAEs from Day 1 through Day 28 postvaccination

Secondary Safety Endpoints

- Solicited injection-site AEs of injection-site pain, injection-site erythema, and injection-site swelling from Day 1 through Day 5 postvaccination
- Solicited systemic AEs of rash, headache, fatigue (tiredness), myalgia (muscle pain), and arthralgia (joint pain) from Day 1 through Day 28 postvaccination

Additional Safety Endpoints

- Unsolicited AEs from Day 1 through Day 28 postvaccination
- Elevated temperature ($\geq 100.4^{\circ}\text{F}$ [38.0°C] oral equivalent) from Day 1 through Day 28 postvaccination
- All MAAEs, SAEs, and deaths through completion of study participation

9.5 Analysis Populations

9.5.1 Immunogenicity Analysis Populations

The Per-Protocol population will serve as the primary population for the analysis of the immunogenicity data in this study. The Per-Protocol population excludes participants due to deviations from the protocol that may substantially affect the results of the primary immunogenicity endpoints. Potential deviations that may result in the exclusion of a participant from the PP population for all immunogenicity analyses include:

- Prevaccination baseline blood sample test result is seropositive for any of the 4 dengue serotypes by VRNT. Seropositivity will be defined as having VRNT at or above the LLOQ of the assay.
- Failure to receive correct clinical material as per randomization schedule
- Receipt of prohibited medication or prohibited vaccine before study vaccination or through Day 28 postvaccination.
- Collection of blood sample at the timepoint for the analysis outside of the pre-specified window, as described in Section 1.3

The final determination on protocol deviations, and thereby the composition of the PP population, will be made before the unblinding of the database and will be documented in a separate memo. The key immunogenicity analyses will also be performed using the Full Analysis Set (FAS) population, which consists of all randomized participants who receive

study vaccination and have at least 1 valid serology result. Participants will be included in the vaccination group that they are randomized for the analysis of immunogenicity data using the FAS population. No adjustment will be made for missing data.

9.5.2 Safety Analysis Populations

The All Participants as Treated (ApaT) population will be used for the analysis of safety data in this study. The ApaT population consists of all randomized participants who received at least 1 dose of study vaccine/placebo. Participants will be included in the vaccination group corresponding to the study vaccine/placebo they actually received for the analysis of safety data using the ApaT population. For most participants this will be the vaccination group to which they are randomized.

9.6 Statistical Methods

This section describes the statistical methods that address the primary and secondary objectives. Statistical methods related to exploratory objectives will be further described in the sSAP. The key immunogenicity analyses to be performed are summarized in [Table 4](#) (Section 9.6.1). The safety analyses are summarized in Section 9.6.2. Unless otherwise stated, all statistical tests will be conducted at the $\alpha=0.05$ (2-sided) level.

9.6.1 Statistical Methods for Immunogenicity Analyses

The primary hypothesis of non-inferiority of GMTs for each dengue serotype (DENV1, DENV2, DENV3, and DENV4) will be addressed by 4 one-sided tests of non-inferiority (one corresponding to each dengue serotype) conducted at $\alpha=0.025$ level (1-sided). For each dengue serotype, the hypotheses to be tested are:

$$H_0: \text{GMT}_x/\text{GMT}_y \leq 0.67$$

Versus

$$H_1: \text{GMT}_x/\text{GMT}_y > 0.67$$

where GMT_x represents the GMT at 28 days postvaccination in the V181 Low Potency Level group and GMT_y represents the GMT at Day 28 postvaccination in the V181 Mid Potency Level group. Estimation of the GMT ratios and computation of the corresponding 95% CIs will be calculated using t-distribution with the variance estimate from a linear model utilizing the log-transformed antibody titers as the response and a single term for vaccination group. The point estimates will be calculated by exponentiating the estimates of the mean of the natural log values and the CIs will be derived by exponentiating the CIs of the mean of the natural log values based on the model. The statistical criterion for non-inferiority requires that the lower bound of two-sided 95% confidence interval of GMT ratio (V181 Low Potency Level vs. V181 Mid Potency Level) being greater than 0.67.

CCI

CCI

[Clopper, C. J. 1934].

Table 4 Analysis Strategy for Immunogenicity Variables

Endpoint/Variable (Description, Time Point)	Primary vs. Supportive Approach ^a	Statistical Method ^b	Analysis Population	Missing Data Approach
Primary Endpoint				
Dengue virus-neutralizing antibody GMTs for each of the 4 dengue serotypes at Day 28 postvaccination as measured by VRNT	P S	t-distribution with the variance estimate from a linear model ^b (estimate, 95% CI, p-value)	PP FAS	Missing data will not be imputed

CI = confidence interval; FAS = Full Analysis Set; GMT = Geometric Mean Titer; PP = Per-Protocol

^a P=Primary approach; S=Supportive approach.

^b Estimation of the dengue virus-neutralizing antibody GMTs and computation of the corresponding 95% CIs will be calculated using t-distribution with the variance estimate from a linear model utilizing the log-transformed antibody titers as the response and a single term for vaccination group.

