9.9 Sample Size and Power Calculations

9.9.1 Sample Size and Power for Immunogenicity Analyses

This study will randomize participants in a 2:4:4:1 ratio into the 4 vaccination groups (V181 High Potency Level Group, V181 Mid Potency Level Group, V181 Low Potency Level Group, and Placebo). The overall sample size will be approximately 1265 with 230 participants in the High Potency Level Group, 460 participants in each of the Mid and Low Potency Level Groups, and 115 participants in the placebo group. The study has an overall power of >95% to establish that the V181 Low Potency Level is non-inferior to the V181 Mid Potency Level for all four serotypes at an overall one-sided, 2.5% alpha-level. The power and sample size are based on the following assumptions: 1) an approximately 15% non-evaluable rate, 2) the non-inferiority margin of 0.67, 3) the true GMT ratio is assumed to be 1, and 4) the standard deviation of the natural-log titers is estimated to be 1.25 for each dengue serotype based on previous clinical and assay data. Given these assumptions, using the most conservative standard deviation, the lowest estimated GMT ratio that would meet a lower bound criterion of 0.67 is approximately 0.78.

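### The model for the primary Low/Mid interval is not restricted to Low and Mid; if placebo enters the residual variance, one-sided type I error could be about 3% instead of 2.5%

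*Combined protocol and SAP*

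**What the plan says.** Section 9.6.1 tests non-inferiority of Low to Mid for each serotype at one-sided 0.025. The interval uses a t-distribution with the "variance estimate from a linear model utilizing the log-transformed antibody titers as the response and a single term for vaccination group". Section 9.1 describes the same analysis, "using a linear model with the log-transformed antibody titer as the response and a single term for vaccination group", and Table 4 footnote b applies that model to the group GMTs and their intervals. None of the three places lists the groups in the fit, and the visible text offers no unequal-variance method.

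Elsewhere the plan treats placebo as a vaccination group. Section 9.9.1: "This study will randomize participants in a 2:4:4:1 ratio into the 4 vaccination groups", with placebo named as the fourth. Section 4.2.1.1 has Day 28 specimens taken from all 1265 participants. The potential per-protocol exclusions in Section 9.5.1 do not remove placebo, but they do include this one: "Prevaccination baseline blood sample test result is seropositive for any of the 4 dengue serotypes by VRNT".

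Section 9.9.1 claims joint power above 95% "for all four serotypes at an overall one-sided, 2.5% alpha-level".

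**The concern.** A residual variance pooled over several groups is valid for a two-group contrast only if those groups share a variance. Placebo probably does not. The study runs in non-endemic countries (Section 4.2.2). Known dengue or zika infection and prior dengue vaccination are exclusions (Section 5.2). The placebo dose strength is 0 PFU (Table 1), and baseline seropositivity is a listed ground for leaving the per-protocol population. Most placebo titers at Day 28 should therefore fall below the LLOQ.

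An arm with almost no spread adds degrees of freedom but hardly any sum of squares. It pulls down the mean square, shortens the Low/Mid interval and makes non-inferiority easier to declare than the stated level allows. A larger trial would not cure this, because the bias depends on the allocation and the variance ratios. The comparison affected is the only hypothesis test in the plan, and its result is meant to support potency release specifications.

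**Working it through.** **Inputs from Section 9.9.1**
- "the non-inferiority margin of 0.67": −ln 0.67 = 0.4005.
- "the true GMT ratio is assumed to be 1".
- SD of natural-log titer 1.25 for each serotype, not broken down by group.
- About 15% non-evaluable: 460 → 391 (Low and Mid each), 230 → about 196 (High), 115 → about 98 (placebo).

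**Assumed, because not in the documents**
- Placebo SD between 0 and 0.625 (0 to 50% of 1.25). The documents also give no numerical value for titers below the LLOQ.
- High-arm SD 1.25, then varied.

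**1. The plan's own power figure, two-group variance**
- SE = 1.25 × √(2/391) = 0.0894.
- Power per serotype = Φ(0.4005/0.0894 − 1.96) = Φ(2.52) = 99.4%.
- All four, taken as independent: 0.9941⁴ = 97.7%.

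The stated figure of more than 95% reproduces.

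**2. Variance pooled over four groups, placebo SD 0**
- Residual df = 391 + 391 + 196 + 98 − 4 = 1072.
- Pooled variance = (390 + 390 + 195) × 1.5625 / 1072 = 1.421, so pooled SD = 1.19.
- Ratio to the true Low/Mid SD = √(975/1072) = 0.954. The interval is about 4.6% too short.
- One-sided error = 1 − Φ(1.962 × 0.9537) = 1 − Φ(1.871) = 3.07%.
- Two-sided coverage = 100% − 2 × 3.07% = 93.9%.

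A simulation with 2,000,000 replicates gives 3.08% for the four-group fit. Fits to Low and Mid only give 2.49% to 2.52%.

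**3. Sensitivity to the two unknown SDs**

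Ratio = √[(780 + 195 r_H² + 97 r_P²)/1072], where r_H and r_P are the High and placebo SDs divided by 1.25.

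| Placebo SD | High SD | Ratio | One-sided error |
|---|---|---|---|
| 0 | 1.25 | 0.954 | 3.07% |
| 0.3125 | 1.25 | 0.957 | 3.03% |
| 0.625 | 1.25 | 0.965 | 2.91% |
| 1.25 | 1.25 | 1.000 | 2.5% |
| 0 | 1.0 | 0.919 | 3.57% |
| 0 | 1.5 | 0.995 | 2.55% |

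With placebo SD 0, exact cancellation needs r_H = √((195 + 97)/195) = 1.22, a High SD of about 1.53.

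**4. Overall error.** All four serotypes must pass. The overall error therefore cannot exceed the single-serotype value, and it approaches that value when one serotype sits at the margin and the others are almost certain to pass. With the other three at a true ratio of 1 and independent, it is 3.02%.

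**5. Effect on the decision and on power (placebo SD 0, High SD 1.25).** The smallest passing GMT ratio falls from 0.799 to 0.792. Power per serotype under the four-group fit is Φ(4.480 − 1.871) = 99.55%, or 98.2% jointly. A Low and Mid fit gives 97.7%.

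**The case against.** The strongest reply is that Section 9.6.1 can be followed word for word with a model fitted to Low and Mid only. Its hypotheses name just those two groups, and Section 9.1 introduces the model for the Low/Mid objective. The counts of four groups and of 1265 specimens describe randomization and sampling, not the model. Placebo's stated roles are blinding and safety control. All of this stands: the four-group fit is the natural literal reading, but not the only one.

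It is also true that no document gives a placebo SD or a High-arm SD, that baseline seropositivity is only a potential ground for exclusion, and that the excess is modest. In the supportive FAS analysis, baseline seropositives may remain, so placebo variance need not be near zero there.

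A reader might infer more than the documents support:
- **That the trial's type I error is known to exceed 2.5%.** That would need the four-group fit, a small placebo SD and a High-arm SD not large enough to offset it. None of these is stated.
- **That the High arm must make matters worse.** It does at SD 1.0, but near 1.53 it cancels the placebo effect.
- **That the approximate 0.78 in Section 9.9.1, the lowest passing GMT ratio, shows a four-group variance was planned.** A four-group variance with 460 per arm and placebo SD 0 does give 0.782. But 460 per arm with a margin of 2/3 gives 0.784, and 391 per arm with z = 1.645 gives 0.776. The match identifies nothing.

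What the reply does not remove is that an analyst who pooled placebo would be complying with the text as written.

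**Conclusion.** The concern holds in conditional form. The plan leaves the source of the primary variance open, and its most natural reading lets placebo, and also High, influence an interval that concerns only Low and Mid. On that reading, with SD 1.25 in all V181 arms and placebo SD between 0 and 0.625, one-sided error is about 3.1% to 2.9% per serotype. That is also the maximum overall error under the all-four rule. With placebo SD 0 it would be about 3.6% if the High SD were 1.0, and about 2.5% if it were about 1.5. The evaluable numbers rest on the plan's 15% loss; the placebo and High SDs are assumptions.

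The excess is too small, and too dependent on unstated variances, to rank as must-fix. It is a should-fix correction, because the stated level should not depend on arms outside the comparison and the remedy is nearly free.

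**What to change.** Before unblinding, state in Sections 9.1 and 9.6.1 and in Table 4 footnote b that the primary Low/Mid comparison is fitted to the Low and Mid groups only, or uses group-specific variances (Welch/Satterthwaite). State also that GMT intervals for the other groups use their own variances. Under the four-group fit, a placebo arm with constant titers would still be given an interval of about 0.79 to 1.27 times its GMT: exp(±1.962 × 1.19/√98).

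The wording cost is a sentence in each place. Section 9 requires a protocol amendment if primary methods change after the study has begun, so the text should go through that route where it applies. The statistical cost is not quite zero: relative to a four-group fit with placebo SD 0, joint power falls from about 98.2% to 97.7% (serotypes taken as independent), still above the claimed 95%. Sample size and data collection do not change.

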Solicited AEs listed above and unsolicited AEs (including MAAEs and SAEs) will be collected Day 1 through Day 28. Following Day 28 postvaccination, MAAEs, SAEs (regardless of causality), and deaths (due to any cause) will be collected through Month 12 postvaccination.

Participant safety will be monitored by an eDMC that will perform periodic reviews of safety data throughout the study (Appendix 1). Details will be provided in the eDMC charter.

Blood samples for the assessment of immune responses will be collected from all participants before vaccination on Day 1 and at the Day 28 and Month 12 postvaccination time points. Participants in each treatment group will be randomized in a centralized process so that half of the participants in each group have blood samples collected at Month 3 and the other half at Month 6. Participants who are not scheduled to have blood draws as per their assigned schedules, will have telephone visits. As this study will be conducted in non-endemic countries, it is expected that the baseline serostatus for the majority of participants will be dengue-seronegative. Therefore, screening for dengue serostatus will not be conducted. The final determination of baseline serostatus for the purpose of the primary analysis will be by the VRNT.

In addition to safety and immunogenicity assessments, blood samples for ^{CCI} ██████████ testing will be obtained at the Day 7 and Day 12 postvaccination time points.

Serum samples from both, the immunogenicity and ^{CCI} ██████████ blood draws, will each be aliquoted in 2 tubes. One tube will be shipped to a prespecified central laboratory and 1 tube will remain at the site as a back-up sample in case the main sample is destroyed in any way. The Sponsor will notify the site when the back-up samples can be shipped to the laboratory. Refer to the Investigator Study File Binder for guidance regarding sample blood volumes and other laboratory procedures.

The primary safety and immunogenicity analyses will be conducted at the Day 28 postvaccination time point to support the establishment of the potency release specifications for V181. A CSR will be written to present the study results from this time period. Immunogenicity and safety results from the Day 28 through Month 12 postvaccination time period will be summarized in a final, separate study report (see Section 9.2).

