9.10 Subgroup Analyses

The subgroup analyses will be comprised of descriptive summary statistics for immunogenicity by gender and age. Further details of subgroup analyses will be documented in the ssAP.

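### The supportive FAS analysis keeps baseline-seropositive participants but has no term for Day 1 dengue serostatus; adding one is an optional precision gain, not the correction of an error

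*Combined protocol and SAP*

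**What the plan says.** Section 9.6.1 bases the GMT ratio and its 95% CI on "a linear model utilizing the log-transformed antibody titers as the response and a single term for vaccination group". Table 4 (with footnote b) applies that model to the PP population as the primary approach and to the FAS as the supportive one; Section 9.1 summarizes the same model.

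Section 9.5.1 lists baseline seropositivity for any serotype by VRNT among the deviations that may remove a participant from the PP population. It then adds: "The key immunogenicity analyses will also be performed using the Full Analysis Set (FAS) population". The FAS needs randomization, vaccination and at least one valid serology result. It carries no serostatus condition.

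Section 4.1 says that "Blood samples for the assessment of immune responses will be collected from all participants before vaccination on Day 1", that serostatus is not screened at entry, and that most participants are expected to be seronegative. Sections 2.1 and 4.2.1.1 justify the seronegative focus on the ground that prior dengue immunity could augment the response and influence the results.

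Section 6.3.2 provides no stratification. Section 9.10 plans "descriptive summary statistics for immunogenicity by gender and age". Section 2.1 does not expect immunogenicity to differ by age in this population.

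**The concern.** The protocol names baseline dengue immunity as something that changes the response and removes it from the primary population for that reason. The supportive analysis then brings the seropositive participants back under a model with no baseline term, although the variable is already measured on everyone.

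Two things are at stake, both limited to the FAS. First, any Day 28 titer difference between seropositive and seronegative participants goes into the residual variance and widens the interval. Second, a chance imbalance in serostatus between the Low and Mid groups moves the unadjusted FAS ratio. The PP and FAS results could then look different for a reason unrelated to potency.

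**Working it through.** **Inputs from the plan (Section 9.9.1).** 460 randomized per group in Low and Mid; about 15% non-evaluable, so 460 × 0.85 = 391 per group; "the non-inferiority margin of 0.67"; "the true GMT ratio is assumed to be 1"; and "the standard deviation of the natural-log titers is estimated to be 1.25 for each dengue serotype". Section 9.6.1 tests each serotype at one-sided 0.025, and Section 9.8 requires all four to succeed.

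**Step 1: reproduce the plan's power.**
- SE of the log ratio = 1.25 × √(2/391) = 0.0894.
- Distance to the margin = −ln 0.67 = 0.4005, and 0.4005/0.0894 = 4.48.
- Power per serotype from the noncentral t with 780 df = 0.9940.
- All four, treated as independent: 0.9940⁴ ≈ 0.976.

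The stated figure of more than 95% is reproduced for the unadjusted model.

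**Step 2: FAS, gain from a serostatus term.** Let f be the seropositive share, d the shift in mean natural-log Day 28 titer among seropositives, and 1.25 the SD within each serostatus group. Unmodelled, serostatus adds f(1−f)d² to a variance of 1.25² = 1.5625. Then R² = f(1−f)d² / [f(1−f)d² + 1.5625], and the half-width falls by 1 − √(1−R²). Neither f nor d is in the documents. The assumed range is 1% to 10% for f, and 4- to 8-fold for the shift (d = ln 4 = 1.386 to ln 8 = 2.079).

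| f | Fold | f(1−f)d² | Variance inflation | R² | Half-width narrower by |
|---|---|---|---|---|---|
| 1% | 4 | 0.019 | 1.2% | 0.012 | 0.6% |
| 1% | 8 | 0.043 | 2.7% | 0.027 | 1.3% |
| 2% | 4 | 0.038 | 2.4% | 0.024 | 1.2% |
| 2% | 8 | 0.085 | 5.4% | 0.051 | 2.6% |
| 5% | 4 | 0.091 | 5.8% | 0.055 | 2.8% |
| 5% | 8 | 0.205 | 13.1% | 0.116 | 6.0% |
| 10% | 4 | 0.173 | 11.1% | 0.100 | 5.1% |
| 10% | 8 | 0.389 | 24.9% | 0.199 | 10.5% |

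In the most favorable row, with all 460 per group in the FAS and an observed ratio of 1, the half-width on the log scale falls from 0.181 to 0.162. The lower bound moves from 0.835 to 0.851. Both are far above 0.67.

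**Step 3: FAS, effect of chance imbalance.** The 95% limit for a chance difference in seropositive share is 1.96 × √(2f(1−f)/460).
- f = 5%, 4-fold: limit 0.028; 0.028 × 1.386 = 0.039, a shift of about 4% in the unadjusted ratio.
- f = 10%, 8-fold: limit 0.039; 0.039 × 2.079 = 0.081, a shift of about 8%.

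**Step 4: PP, what age and sex could add.** Replace 1.25 by 1.25 × √(1−R²) and deduct 2 df. R² is again an assumption.

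| R² | Half-width | Joint power, true ratio 1 | 0.95 | 0.90 |
|---|---|---|---|---|
| 0 | 0.1755 | 97.6% | 90.0% | 68.4% |
| 0.02 | 0.1737 | 97.9% | 90.8% | 70.0% |
| 0.05 | 0.1710 | 98.3% | 92.0% | 72.4% |

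For scale, a 1.25-fold GMT difference between equally sized sexes gives R² = 0.25 × (ln 1.25)²/1.5625 ≈ 0.008, which narrows the half-width by 0.4%.

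**The case against.** The strongest reply is that nothing is wrong. Under unstratified randomization a group-only model gives a valid GMT ratio and interval, and the interval already allows for chance imbalance. The SD of 1.25 is described as that of the log titers, not as a residual SD, so the power calculation and the analysis match. All of that stands.

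The FAS is also only supportive, and few seropositives may be enrolled: sites are in non-endemic regions (Section 4.1), and known dengue or Zika infection and prior dengue vaccination are exclusions (Section 5.2). That stands too, and it is why the range above starts at 1%. It does not remove the point, because serostatus is not screened and the protocol treats it as affecting the response.

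A further objection is that different models in PP and FAS would mix a change of population with a change of model. This is fair, and it is answered by also reporting the unadjusted FAS ratio. A linear term in log Day 1 titer would be awkward with most values below the LLOQ; a two-level serostatus term avoids that.

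A reader might infer more: that leaving out age and sex makes the primary non-inferiority intervals wider than the collected data require. The documents do not support this. They give no figure for how far age or sex predicts titer, Section 2.1 expects no age difference, and the subgroup summaries in Section 9.10 are descriptive and do not show that the sponsor regards either as prognostic. The larger power gains in Step 4 appear only at true ratios below 1, which is not the planning assumption.

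**Conclusion.** The point holds for the FAS, as a minor and optional improvement. A baseline serostatus term would narrow the FAS half-width by about 0.6% to 10.5%, if 1% to 10% of participants are seropositive with 4- to 8-fold higher Day 28 titers. It would also take out most of a chance shift that could reach 4% to 8% in the 5% to 10% scenarios. These sizes rest wholly on assumed values; with almost no seropositives the gain is close to nil.

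For the decisive PP analysis no loss of precision is shown. At the planned ratio of 1, joint power is about 97.6% without covariates, and an assumed R² of 2% to 5% raises it by only 0.3 to 0.7 points. The group-only model is valid in both populations, and the non-inferiority conclusion does not depend on this change.

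**What to change.** In Section 9.6.1 and Table 4 footnote b, add baseline dengue serostatus to the FAS model: seropositive to any serotype versus seronegative, by the VRNT LLOQ as already defined in Section 9.5.1. Report the adjusted GMT ratio with its 95% CI, and keep the unadjusted FAS ratio as a sensitivity analysis so that PP and FAS can still be compared under one model. State how FAS participants without a valid Day 1 result are handled, since the FAS definition does not require one. Adjust the summary in Section 9.1 to match.

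The PP model can stay as it is; adding age and sex there is optional.

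The cost is a few lines of text and one degree of freedom out of several hundred, with no new data. Because the model serves the primary hypothesis, the safe course is a protocol amendment before unblinding, as Section 9 requires for changes to methods related to that hypothesis. It could be made together with another amendment.
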